7.2.2 Dose and schedule

The first dose of study drug should be administered on Day 1 (week 0), and will mark the beginning of the treatment period. This should correspond to a day when the next dose of erythropoietin analogue would have been administered in patient currently treated with erythropoietin analogue. All randomization visit study procedures including laboratory blood draws are to be completed prior to administration of the first dose of study drug. All dose adjustments should be based on Hb values using Hemocue, a point-of-care device, at visits specified in [Table 1](#). Hb values will be recorded in the eCRF (screening) and IWRS (during treatment period).

Missed dose should not be replaced.

7.2.3 Dosing of Roxadustat

Roxadustat will be dosed orally three times a week (TIW) throughout the treatment period unless dose reduction is required based on Hb levels. For hemodialysis patients, it is recommended that roxadustat is taken after completion of the hemodialysis session.

7.2.3.1 Patients treated with erythropoietin analogue at study entry

Patients randomized to roxadustat will discontinue any prior erythropoietin analogue therapy and start roxadustat. The starting dose of roxadustat will be based on the current erythropoietin analogue dose at screening visit 1 ([Table 4](#)). If the mean hemoglobin during the screening phase (e.g. the average of central laboratory values at visit 1 and visit 2 or the average of the values at visit 2 and the retest of visit 2 value, if applicable) is less than 10 g/dL, the starting dose will be

increased by one dose step. For example, a patient being treated with an average of 10,000 IU of epoetin alfa per week with a Hb value of 11 g/dL during the screening period would take roxadustat 150 mg orally, three times a week (TIW). In contrast, a patient being treated with an average of 10,000 IU of epoetin alfa per week who had a screening Hb of 9 g/dL during the screening period would take roxadustat 200 mg orally TIW.

Table 4 Initial dosing of roxadustat for patients treated with an erythropoietin analogue at study entry

Epoetin alfa or beta^a (IU/week)	Darbepoetin alfa^{a,b} (µg/week)	Mircera^{®c} (µg/month)	Roxadustat dose^d (mg/dose) TIW
<5,000	<25	<80	70
5,000 to ≤8,000	25-40	80-120	100
>8,000 to 16,000	40-80	120-200	150
>16,000	>80	>200	200 ^e

a Current weekly dose at screening visit 1

b If darbepoetin is used once every 2 weeks, use half dose given every 2 weeks to determine the roxadustat starting dose.

c Current monthly dose at screening visit 1.

d Starting dose will be 1 step higher if the mean central Hb value from the last 2 screening visits is <10 g/dL.

e If the initial dose of 200 mg exceeds the maximum dose of 3.0 mg/kg, then 150 mg should be chosen as the starting dose

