1.2.2 Rationale for doses

Starting doses of roxadustat were studied in three ways in the Phase 2 program: mg per kg weight-based dosing, tiered weight-based dosing or a fixed starting dose regardless of weight.

Dose adjustments were allowed at regular 4-week intervals to maintain, increase or decrease the dose according to pre-specified rules. Additional rules were provided to minimize excessive erythropoiesis. These dose adjustment rules are adopted in this study with minor modifications.

For patients treated with an erythropoietin analogue at study entry, selection of initial roxadustat dose in this study will utilize a conversion table based on the patient's current erythropoietin analogue dose at screening visit 1. Patients not currently treated with erythropoietin analogue will initiate roxadustat using a tiered weight-based dose dosing scheme. Patients with dry weights between 45 and 70 kg will receive 70 mg of roxadustat as starting dose. Patients with dry weights between 71 and 160 kg will receive 100 mg of roxadustat for initial dosing.

Doses will be administered at a frequency of three times a week (TIW) throughout the study treatment period unless downward dose adjustment requires a change to twice or once weekly.

In the event of excessive erythropoiesis, the dose may be adjusted at any time. The maximum dose of roxadustat allowed will be the lower of 3.0 mg/kg or 400 mg per dose.

Patients randomized to the epoetin alfa group will receive an epoetin alfa dosing regimen with initial and subsequent dose adjustments in accordance with accepted clinical practice guidelines and approved prescribing information for epoetin alfa. The initial dose of epoetin alfa will be selected based on the erythropoietin analogue regimen used prior to the entry into the study. Patients who were not receiving an erythropoietin analogue at study entry will initially receive epoetin alfa at a dose of 50 IU/kg three times weekly. Adjustments in the total weekly dose or frequency of epoetin alfa dosing should subsequently be made to achieve an Hb of 11 g/dL and maintain Hb levels of 11 ± 1 g/dL.

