3.1 Inclusion criteria

For inclusion in the study subjects should fulfil the following criteria:

1. Provision of Informed Consent prior to any study specific procedures
2. Age \geq 18 years at screening visit 1
3. **Previous versions of the protocol prior to US amendment ver 6.0 and outside of US amendment ver 7.0:**
Receiving or initiating hemodialysis or peritoneal dialysis for treatment of native kidney end-stage renal disease (ESRD) at least 30 days prior to visit 1. Patients treated with hemodialysis must have access consisting of an arteriovenous fistula, AV graft, or tunneled (permanent) catheter. Patients on peritoneal dialysis must have a functioning peritoneal dialysis catheter in place.

Starting with US amendment ver. 6.0 and outside of US amendment ver 7.0 (changed to recruit incident dialysis patients only):

Receiving or initiating hemodialysis or peritoneal dialysis for treatment of native kidney end-stage renal disease (ESRD) for a minimum of 2 weeks and a maximum of 4 months prior to randomization. Patients treated with hemodialysis must have access consisting of an arteriovenous fistula, AV graft, or tunneled (permanent) catheter. Patients on peritoneal dialysis must have a functioning peritoneal dialysis catheter in place.

4. Two central laboratory Hb values during the screening period, obtained at least 7 days apart, must be <12 g/dL in patients currently treated with an erythropoietin analogue or <10 g/dL in patients not currently treated with an erythropoietin analogue. Patients are considered not currently treated if they have not received either Mircera® for at least 8 weeks or any other erythropoietin analogue for at least 4 weeks prior to visit 1.
5. Ferritin \geq 100 ng/mL at randomization (obtained from screening visit)
6. TSAT \geq 20% at randomization (obtained from screening visit)
7. Serum folate level \geq lower limit of normal (LLN) at randomization (obtained from screening visit)
8. Serum vitamin B12 level \geq LLN at randomization (obtained from screening visit)
9. Alanine aminotransferase (ALT) and aspartate aminotransferase (AST) \leq 3x upper limit of normal (ULN), and total bilirubin (Tbili) \leq 1.5 x ULN at randomization (obtained from screening visit)
10. Body weight 45 to 160 kg (prescribed dry weight)

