6.5 Overdose

The maximum tolerated dose of roxadustat has not been established in humans. For the purposes of this study, exceeding the maximum allowed dose specified in this CSP (3.0 mg/kg or 400 mg per administration, whichever is lower) represents an overdose.

An overdose with associated AEs is recorded as the AE diagnosis/symptoms on the relevant AE modules in the eCRF and on the Overdose eCRF module.

An overdose without associated symptoms is only reported on the Overdose eCRF module.

If an overdose on an AstraZeneca study drug occurs in the course of the study, then the Investigator or other site personnel inform appropriate AstraZeneca representatives immediately, or **no later than 24 hours** of when he or she becomes aware of it.

The designated AstraZeneca representative works with the Investigator to ensure that all relevant information is provided to AstraZeneca.

For overdoses associated with a SAE, the standard reporting timelines apply, see Section 6.4. For other overdoses, reporting must occur within 30 days.

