7.2 Dose and treatment regimens

7.2.1 Randomization

Eligible patients will be randomized to receive either roxadustat or epoetin alfa in a 1:1 ratio. Randomization schedules will be prospectively prepared. Automated randomization and assignment to treatment arm will be provided by IWRS/IVRS. The randomization in this study will be stratified by country.

The number of tablet bottles (or amount of epoetin alfa supplied by AstraZeneca) that will be dispensed may vary depending on the dose. Dispensation will be managed by IWRS/IVRS. The administration will be detailed on a dosing card. Doses administered will be recorded in the eCRF.

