7.2.3.3 Roxadustat dose adjustments

Roxadustat dose will remain constant during the first 4 weeks of the treatment period, unless a dose reduction is required for excessive erythropoiesis. Dose may be adjusted at week 4 and every 4 weeks thereafter in accordance b to achieve and maintain Hb 11±1 g/dL. Dose adjustment is based on Hb assessed by Hemocue.

Table 6 Roxadustat dose adjustments

Changes in Hb over past 4 weeks	Hb <10.5g/dL	Hb 10.5 to 11.9g/dL	Hb 12.0 to 12.9g/dL	Hb ≥13.0g/dL
<-1.0	↑	↑	No change	Hold, then resume dosing when Hb ≤11.9 g/dL, at a dose that is reduced by two dose steps
-1.0 to 1.0	↑	No change	↓	
>1.0	No change	↓	↓	

Dose Increases and Reductions:
Dose increases (↑) and reductions (↓) are pre-set according to dose steps.
The dose steps are as follows: 20, 40, 50, 70, 100, 150, 200, 250, 300, and 400 mg.

Example: A dose increase at a dose of 70 mg results in 100 mg as the new dose. A dose reduction at a dose 150 mg results in 100 mg as the new dose.

If patients on 20 mg TIW need dose reduction, change frequency to twice a week, i.e. 20 mg administered twice a week. If further dose reduction is needed, reduce frequency to once weekly, i.e. 20 mg administered once a week.
Note: Maximum dose is capped at the lower of 3.0 mg/kg or 400 mg per dose administration.

Dose Adjustment for Excessive Erythroipoiesis:

- If Hb increases by >2.0 g/dL within a 4 week period, the dose should be reduced by one dose step.

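### For some roxadustat patients weighing 45 to <50 kg, Table 4 footnote e names a 150 mg starting dose that is above the 3.0 mg/kg maximum the footnote is meant to apply

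*Protocol*

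**What the plan says.** Table 4 in Protocol Section 7.2.3.1 converts the prior ESA dose into a roxadustat starting dose of 70, 100, 150 or 200 mg. The 200 mg row applies above 16,000 IU/week of epoetin, 80 µg/week of darbepoetin or 200 µg/month of Mircera. Footnote d raises the start by one dose step when mean screening Hb is below 10 g/dL. Footnote e is attached to the 200 mg entry only: "If the initial dose of 200 mg exceeds the maximum dose of 3.0 mg/kg, then 150 mg should be chosen as the starting dose".

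The limit that footnote e refers to is set in Section 1.2.2: "The maximum dose of roxadustat allowed will be the lower of 3.0 mg/kg or 400 mg per dose". The note to Table 6 repeats it. Section 6.5 adds that "exceeding the maximum allowed dose specified in this CSP (3.0 mg/kg or 400 mg per administration, whichever is lower) represents an overdose". Inclusion criterion 10 (Section 3.1) admits dry weights from 45 to 160 kg. Section 7.2.3.3 fixes the available doses: "The dose steps are as follows: 20, 40, 50, 70, 100, 150, 200, 250, 300, and 400 mg".

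**The concern.** Footnote e exists to keep the starting dose within 3.0 mg/kg. It tests 200 mg against that limit, substitutes 150 mg, and does not test 150 mg. At the bottom of the eligible weight range the substitute is also over the limit, so a site that follows the footnote exactly gives a dose that Section 6.5 classes as an overdose. No section says which instruction prevails.

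A starting dose is not a single exposure. Section 7.2.3.3 states: "Roxadustat dose will remain constant during the first 4 weeks of the treatment period", with an exception for excessive erythropoiesis. Section 7.2.3.5 separately requires a hold at Hb of 13.0 g/dL or more. At stake is a dosing rule that contradicts its own safety limit for a small subgroup. The efficacy inference is not at stake.

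**Working it through.** **Inputs.** Cap: the lower of 3.0 mg/kg and 400 mg (Protocol 1.2.2, Table 6 note, 6.5). Eligible dry weight: 45 to 160 kg (3.1). Fallback: 150 mg (Table 4, footnote e). Dose steps: 7.2.3.3. The 400 mg limit binds only above 400/3.0 = 133.3 kg, so here the cap at weight w is 3.0 × w.

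**Where the footnote applies.** 200 mg exceeds 3.0 × w when w < 200/3.0 = 66.7 kg.

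**Where its answer is right.** 150 mg is within the cap when w ≥ 150/3.0 = 50.0 kg. From 50 to <66.7 kg the plan's 150 mg is therefore confirmed: 150/50 = 3.00 mg/kg, falling to 150/66.7 = 2.25 mg/kg.

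**Where it is wrong.** From 45 to <50 kg:

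| Dry weight (kg) | Cap = 3.0 × w (mg) | 150 mg in mg/kg | Excess (mg) | Excess / cap |
|---|---|---|---|---|
| 45 | 135 | 3.33 | 15 | 11.1% |
| 46 | 138 | 3.26 | 12 | 8.7% |
| 47 | 141 | 3.19 | 9 | 6.4% |
| 48 | 144 | 3.13 | 6 | 4.2% |
| 49 | 147 | 3.06 | 3 | 2.0% |
| 49.9 | 149.7 | 3.01 | 0.3 | 0.2% |
| 50 | 150 | 3.00 | 0 | 0% |

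**Highest compliant dose in this band.** No step lies between 100 and 150 mg, so the answer is 100 mg: 100/45 = 2.22 mg/kg and 100/49.9 = 2.00 mg/kg.

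**Who reaches the footnote.** Weight alone is not enough. The patient must be randomized to roxadustat, already on an ESA, and have a Table 4 dose of 200 mg. There are two routes:
- The top ESA row. For epoetin this means more than 16,000/50 = 320 IU/kg/week at 50 kg, and more than 16,000/45 = 356 IU/kg/week at 45 kg.
- The 150 mg row raised one step for low screening Hb, if footnote e is read to cover a dose that footnote d has raised to 200 mg.

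**Worst-case exposure before the week 4 review.** 3 doses/week × 4 weeks = 12 doses, and 12 × 15 mg = 180 mg above the cap in total. This needs a weight of exactly 45 kg and every dose taken. At 49 kg it is 12 × 3 = 36 mg.

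**Patients not on an ESA.** Table 5 gives 70 mg at 45 kg, which is 70/45 = 1.56 mg/kg. The problem does not arise there.

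**The case against.** The strongest reply is that the general cap already governs. It is stated without exception in Section 1.2.2, repeated under Table 6 and used again in Section 6.5, so a site that respects it would not give 150 mg to a 46 kg patient. This reply disposes of a wider charge against Table 4. A reader might infer that the plain 150 mg row, the 100 mg row raised one step, and the unstated order of footnotes d and e are contradictions too. They are not: Table 4 is silent there and the general cap fills the gap. Footnote e is different. It is the instruction that applies the cap to the starting dose, and it names the dose to give. A site that has just compared 200 mg with 3.0 mg/kg and followed the footnote has reason to think the cap is met.

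The second reply is that the excess is small and not shown to be harmful. That stands. The version history says the cap was lowered from 3.5 mg/kg to align with the non-dialysis programme, and 3.33 mg/kg is below that former figure. The documents give no safety threshold at 3.0 mg/kg.

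The third reply is that the dose may never have reached a patient. Section 7.2.1 says: "Dispensation will be managed by IWRS/IVRS". The documents do not say whether that system checked the cap.

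A reader might also infer that such overdoses would go unrecorded, because "An overdose without associated symptoms is only reported on the Overdose eCRF module". The documents do not support this. The same section requires the site to inform the sponsor within 24 hours of becoming aware of an overdose, and sets a 30-day limit for overdoses not associated with an SAE. Whether sites recognised these doses as overdoses cannot be known from the plan.

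**Conclusion.** Footnote e is wrong as written, and the matter is minor. For ESA-treated roxadustat patients of 45 to <50 kg whose Table 4 dose is 200 mg, it prescribes 3.01 to 3.33 mg/kg against a maximum of 3.0 mg/kg. The excess is at most 15 mg per dose (11.1%), at 45 kg, and shrinks to nothing at 50 kg.

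The arithmetic is exact, on the assumption that the cap is applied to dry weight, as the eligibility criterion and Table 5 are. The number of patients is unknown, because the documents give no joint distribution of weight and prior ESA dose. It could be zero. It would be too strong to say that all eligible patients of 45 to <50 kg are affected, since the prior-ESA condition must also hold.

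Nor do the documents support an effect on the analysis. The starting dose is open to adjustment from week 4, well before the week 28 to 36 and week 28 to 52 Hb windows, and overdose is not among the important protocol deviations in SAP Table 1.

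**What to change.** Replace footnote e with: *The starting dose is the lower of the table dose after any footnote d increase and the highest dose step not exceeding 3.0 mg/kg.* This gives a ceiling of 100 mg at 45 to <50 kg, 150 mg at 50 to <66.7 kg and 200 mg at 66.7 to <83.3 kg. From 250/3.0 = 83.3 kg upward the cap no longer binds, because 250 mg is the highest start that Table 4 and footnote d can produce. The rule also settles the order of footnotes d and e.

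The change costs one footnote. Its downside is a start one third lower (100 instead of 150 mg) for a few patients with high prior ESA need. Dose review begins at week 4, but while weight stays below 50 kg the next step up is 150 mg, which the Table 6 note already rules out. The clinical team should therefore confirm that 100 mg is acceptable.

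Version 8.0 is dated 19 September 2018 and Section 9.3 estimates study end by Q3 2018, so enrolment is probably complete. In that case the useful step is a data check: divide each roxadustat subject's recorded starting dose by dry weight, flag values above 3.0 mg/kg, and reconcile them with the Overdose eCRF module. Dry weight is collected at randomization (Protocol Table 1) and doses given are in the eCRF (Section 7.2.1), so this needs one derived variable and no new data. It would also find starts above the cap that arose by any other route.

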7.2.3.2 Patients not treated with erythropoietin analogue at study entry

The initial roxadustat dose (administered TIW) is based on a tiered, weight-based dosing scheme (Table 5). For example, a patient that has a dry weight of 80 kg would initiate roxadustat treatment with 100 mg orally TIW.

Table 5 Initial dosing of roxadustat dose for patients not taking erythropoietin analogue at study entry

Dry Weight (kg)	Roxadustat dose, mg TIW
45-70	70
>70-160	100

7.2.3.3 Roxadustat dose adjustments

Roxadustat dose will remain constant during the first 4 weeks of the treatment period, unless a dose reduction is required for excessive erythropoiesis. Dose may be adjusted at week 4 and every 4 weeks thereafter in accordance b to achieve and maintain Hb 11±1 g/dL. Dose adjustment is based on Hb assessed by Hemocue.

Table 6 Roxadustat dose adjustments

Changes in Hb over past 4 weeks	Hb <10.5g/dL	Hb 10.5 to 11.9g/dL	Hb 12.0 to 12.9g/dL	Hb ≥13.0g/dL
<-1.0	↑	↑	No change	Hold, then resume dosing when Hb ≤11.9 g/dL, at a dose that is reduced by two dose steps
-1.0 to 1.0	↑	No change	↓	
>1.0	No change	↓	↓	

Dose Increases and Reductions:
Dose increases (↑) and reductions (↓) are pre-set according to dose steps.
The dose steps are as follows: 20, 40, 50, 70, 100, 150, 200, 250, 300, and 400 mg.

Example: A dose increase at a dose of 70 mg results in 100 mg as the new dose. A dose reduction at a dose 150 mg results in 100 mg as the new dose.

If patients on 20 mg TIW need dose reduction, change frequency to twice a week, i.e. 20 mg administered twice a week. If further dose reduction is needed, reduce frequency to once weekly, i.e. 20 mg administered once a week.
Note: Maximum dose is capped at the lower of 3.0 mg/kg or 400 mg per dose administration.

Dose Adjustment for Excessive Erythroipoiesis:

- If Hb increases by >2.0 g/dL within a 4 week period, the dose should be reduced by one dose step.

7.2.3.4 Dose adjustment for excessive erythroipoiesis

Excessive erythroipoiesis is defined in Table 6. In the event of excessive erythroipoiesis, the dose may be adjusted, even on visits without a dose adjustment review. In such cases, dose adjustment reviews are then resumed at 4-week intervals. If a dose adjustment review is scheduled on week 18, then the next dose adjustment review will be scheduled on week 24, since there is no scheduled visit on week 22.

7.2.3.5 Dose adjustments for excessive Hb ≥ 13.0g/dL

In the event of Hb value ≥13.0g/dL, dosing will immediately be put on hold. Resume dosing at a subsequent visit when Hb ≤11.9 g/dL, at a dose that is reduced by two dose steps. After dosing has been resumed, the dose adjustment reviews are then continued at 4-week intervals following the same principle as for excessive erythroipoiesis.

7.2.4 Dosing of epoetin alfa (active control)

7.2.4.1 Patients treated with epoetin alfa or beta at study entry

All patients who are randomized to the epoetin alfa group should initially receive epoetin alfa TIW with the exception of patients who were treated with epoetin alfa using a less frequent dosing regimen (for example, twice weekly dosing) prior to study entry. The initial dose of epoetin alfa will be the actual dose given at the time of screening visit 1.

7.2.4.2 Patients treated with darbepoetin alfa or Mircer[®] at study entry

Patients treated with darbepoetin alfa or Mircer[®] who are randomized to the epoetin alfa group will initially receive epoetin alfa at doses based on a conversion factor as described in [Table 7](#).

Table 7 Initial dosing of epoetin alfa for patients treated with darbepoetin alfa or Mircer[®] at study entry

	Conversion Ratio	Examples of converted initial epoetin alfa dose (IU/week)^d
Darbepoetin alfa (µg/week) ^a	x 200	40 µg/week x 200 = 8,000 IU/week
Mircera [®] (µg/month) ^b	x 70 to 80 (Lower conversion ratio can be used for lower Mircer [®] dose) ^c	100 µg/month x 70=7,000 IU/week 200 µg/month x 80=16,000 IU/week

a Current weekly dose at screening visit 1

b Current monthly dose at screening visit 1

c Per discretion of investigator

d May be rounded if deemed necessary

7.2.4.3 Patients not treated with erythropoietin at study entry

Patients who are not currently treated with erythropoietin analogue at study entry who are randomized to the epoetin alfa group will be treated with epoetin alfa with an initial dose of 50 IU/kg TIW. Dose adjustments should not occur more frequently than every 4 weeks and be made in a manner consistent with local approved prescribing information for epoetin alfa. In countries where no local guideline is available, Handling Instruction including Summary of Product Characteristics will be provided as guideline for dosing by AstraZeneca.

7.3 Labelling

Labelling of roxadustat and centrally sourced epoetin alfa will be carried out by AstraZeneca or their designee in accordance with current Good Manufacturing Practise (GMP). The labels will fulfil GMP Annex 13 requirements for labelling and local regulatory guidelines. The label text will be translated into local language.

7.4 Storage

All study drugs should be kept in a secure place under appropriate storage conditions. The investigational product label on the bottle specifies the appropriate storage.

7.5 Compliance

The administration of all study drugs (including investigational products) should be recorded in the appropriate sections of the eCRF.

7.6 Accountability

The study drug provided for this study will be used only as directed in the study protocol.

The study personnel will account for all study drugs dispensed to and returned from the patient.

Study site personnel, if applicable, or the AstraZeneca monitor will account for all study drugs received at the site, unused study drugs and for appropriate destruction. Certificates of delivery, destruction and return should be signed. Unused and/or returned investigational products should be destroyed at the site according to local regulations.

